6.1.2 Study Visits 1 to 3: Weeks 4 to 12, Clinic Visit

The subject will return to the study site for a clinic visit as per the schedule of events described in Table 12–1. Concomitant medications and AEs will be reviewed. Weight and vital signs will be measured.

The 3-day voiding diary provided to the subject at her previous visit will be collected and completion verified. The subject will be provided with a new 3-day voiding diary and instructed to complete it within the week preceding her next study visit. The subject will also complete the PGI-S and PGI-I during each site visit. Blood will be drawn for a CMP, CBC, lipid panel, hormone panel, and SHBG tests.

Study drug will be dispensed with administration instructions. The medication identification number assigned to the subject will be noted in the eCRF for study drug accountability. The subject will be reminded to bring all unused study drug (in its original packaging) to her next clinic visit.

A transvaginal ultrasound examination will be performed in subjects with an intact uterus only at Visit 3.

6.1.3 Study Visit 4 Onwards: Week 24 Onwards, Clinic Visit

During the long-term safety period (after Visit 3), the subject will return to the study site for clinic visits. Concomitant medications and AEs will be reviewed. Weight and vital signs will be measured. Blood will be drawn for a CMP, CBC, and lipid panel. Completion of a 3-day voiding diary will be verified.

The hormone panel and SHBG tests will be assessed every 24 weeks only (i.e., every other clinic visit).

A transvaginal ultrasound examination will be performed every 24 weeks (i.e., every other clinic visit) in subjects with an intact uterus. Study drug will be dispensed, with administration instructions, at each clinic visit. The medication identification number assigned to the subject will be noted in the eCRF for study drug accountability. The subject will be reminded to bring all unused study drug (in its original packaging) to her next clinic visit.

The subject will be provided with a new 3-day voiding diary and instructed to complete it within the week preceding her next study visit.

Any subject who prematurely discontinues study or study drug will be asked to return to the study site and complete the end-of-study assessments.

6.1.4 End-of-Study Visit

Approximately 30 days after the last dose of GTx-024, the subject will return to the study site for an end-of-study clinic visit. Unused study drug will be collected. Concomitant medications and AEs will be reviewed. Weight and vital signs will be measured. Blood will be drawn for a CMP, CBC, lipid panel, hormone panel, and SHBG test. Completion of a 3-day voiding diary will be verified.

The subject will complete the PGI-S and PGI-I questionnaires.

The subject will be instructed on the transition to commercial drug or other therapy by the physician.

6.2 Efficacy Assessments

Efficacy assessments will include a 3-day voiding diary, PGI-S, and PGI-I.

6.2.1 Three-Day Voiding Diary

Subjects will record all urinary voids, specifying each episode of urinary leakage, including type (stress or urge). Fluid intake will also be recorded as well as any episode of vaginal discharge or spotting.

In each 3-day voiding diary, subjects are to record voiding data for 3 consecutive days in a paper diary. To be considered valid, each 3-day voiding diary must be recorded within 7 days on either side of a planned visit.

Three-day voiding diaries are reliable measures of the mean number of urinary incontinence episodes per day, incontinence type, mean number of voids per 24 hours, and mean number of voids during sleeping hours.

6.2.2 Patient Global Impression of Severity

The PGI-S is a global rating of subject-reported impression of SUI severity using a 4-point scale (Appendix 12.2). Validity of the PGI-S has been established for application in SUI.

6.2.3 Patient Global Impression of Improvement

The PGI-I is a global rating of subject-reported impression of SUI improvement using a 7-point scale (Appendix 12.3). Validity of the PGI-I has been established for application in SUI.

6.3 Safety Assessments

6.3.1 Adverse Events

6.3.1.1 Definitions of Adverse Events

The investigator is responsible for reporting all AEs that are observed or reported during the study regardless of their possible relationship to study drug or their clinical significance.

An AE is defined as any untoward medical occurrence in a subject enrolled into this study regardless of its causal relationship to study drug. Subjects will be instructed to contact the investigator at any time after randomization if any symptoms develop.

A treatment-emergent AE is defined as any event not present before exposure to study drug or any event already present that worsens in either intensity or frequency after exposure to study drug and within the 30 days following discontinuation of drug treatment.

An SAE is defined as any event that results in one of the following conditions:

- Death
- Life-threatening event (defined as a subject at immediate risk of death at the time of the event)
- An event that requires inpatient hospitalization or prolongation of existing hospitalization
- An event that results in persistent or significant disability/incapacity
- An event that results in a congenital anomaly/birth defect
- Any other important medical event that may not result in death, be life threatening, or require hospitalization may be considered an SAE when, based upon appropriate medical judgment, the event may jeopardize the subject or may require medical or surgical intervention to prevent one of the outcomes listed in this definition. Examples of such medical events include allergic bronchospasm that requires intensive treatment in an emergency room or at home, blood dyscrasias or convulsions that do not result in inpatient hospitalization, or the development of drug dependency or drug abuse

6.3.1.2 Eliciting and Documenting Adverse Events

Adverse events will be assessed beginning at enrollment (date of signed informed consent) through the end of the study.

Serious AEs that occur more than 30 days after the last dose of study drug need not be reported unless the investigator considers them to be related to study drug.

At every study visit, subjects will be asked a standard nonleading question to elicit any medically related changes in their well-being. They will also be asked if they have been hospitalized, had any accidents, used any new medications, or changed concomitant medication regimens (both prescription and OTC medications).

In addition to subject observations, AEs identified from any study data (e.g., laboratory values, physical examination findings) or identified from review of other documents (e.g., subject diaries) that are relevant to subject safety will be documented on the AE page in the eCRF.

6.3.1.3 Reporting Adverse Events

All AEs reported or observed during the study will be recorded on the AE page in the eCRF. Information to be collected includes drug treatment, dose, event term, time of onset, investigator-specified assessment of severity and relationship to study drug, time of resolution of the event, seriousness, any required treatment or evaluations, and outcome. Adverse events resulting from concurrent illnesses, reactions to concurrent illnesses, reactions to concurrent medications, or progression of disease states must also be reported. All AEs will be followed to adequate resolution. The Medical Dictionary for Regulatory Activities (MedDRA) will be used to code all AEs.

Any medical condition that is present at the time that the subject is screened should not be reported as an AE. However, if a pre-existing condition changes in intensity or frequency at any time during the study, it should be recorded as an AE.

Any AE that meets SAE criteria (Section 6.3.1.1) must be entered into the electronic data capture (EDC) system immediately (i.e., within 1 business day) after site personnel first learn of the event. Once the qualifying SAE data are entered, pharmacovigilance will be notified by an email alert, which will contain high-level safety information. Additional safety information will be obtained from the EDC system via applicable eCRF pages. If the EDC system is not available, the site should send a completed paper SAE report form to pharmacovigilance by fax or email:

- Safety fax line: [name] (US toll-free)
- Safety email: [contact]

When the EDC system is again available, the site must enter all applicable information into the EDC system. All supporting source information concerning the SAE (e.g., hospital records) should be provided by fax or email.

If there is a question concerning an SAE, the site needs guidance regarding reporting of an SAE, the site is returning a call from a safety specialist, or the site urgently needs to report an SAE or make pharmacovigilance aware of an SAE, the Safety Hotline should be used:

- Safety [contact] (US toll-free)

If a site makes an initial report of an SAE by the safety hotline, the site must subsequently enter all applicable information into the EDC system immediately thereafter.

6.3.1.4 Assessment of Severity

All AEs will be assessed by the investigator according to National Cancer Institute–Common Terminology Criteria for Adverse Events (NCI-CTCAE) version 4.0. For any AE that is not specifically covered in NCI-CTCAE version 4.0, the criteria that should be used are as follows:

Grade	Description
0	No AE or within normal limits
1	Mild; asymptomatic or mild symptoms; clinical or diagnostic observations only; intervention not indicated
2	Moderate; minimal, local, or noninvasive intervention indicated; limiting age-appropriate instrumental activities of daily living
3	Severe or medically significant but not immediately life-threatening; hospitalization or prolongation of hospitalization indicated; disabling; limiting self-care activities of daily living
4	Life-threatening consequences; urgent intervention indicated

Changes in the severity of an AE should be documented to allow an assessment of the duration of the event at each level of intensity to be performed. Adverse events characterized as intermittent do not require documentation of onset and duration of each episode.

6.3.1.5 Assessment of Causality

The investigator's assessment of an AE's relationship to study drug is part of the documentation process, but it is not a factor in determining what is or is not reported in the study. If there is any doubt as to whether a clinical observation is an AE, the event should be reported.

The relationship or association of the test article in causing or contributing to the AE will be characterized using the following classification and criteria:

Unrelated: This relationship suggests that there is no association between the study drug and the reported event.

Possible: This relationship suggests that treatment with the study drug caused or contributed to the AE, i.e., the event follows a reasonable temporal sequence from the time of drug administration or follows a known response pattern to the study drug but could also have been produced by other factors.

Probable: This relationship suggests that a reasonable temporal sequence of the event with drug administration exists and, based upon the known pharmacological action of the drug, known or previously reported adverse reactions to the drug or class of drugs, or judgment based on the investigator's clinical experience, the association of the event with the study drug seems likely. The event disappears or decreases on cessation or reduction of the dose of study drug.

Definite: This relationship suggests that a definite causal relationship exists between drug administration and the AE, and other conditions (concurrent illness, progression/expression of disease state, or concurrent medication reaction) do not appear to explain the event. The event reappears or worsens if the study drug is re-administered.

6.3.1.6 Follow-Up of Subjects Reporting Adverse Events

All AEs must be reported in detail on the appropriate page in the eCRF and be monitored to satisfactory resolution, until the investigator deems the event to be chronic or not clinically significant, or until the subject is considered to be stable.

6.3.2 Halting Rules

If, in the opinion of the investigator, the participation in the study is or is becoming detrimental to the well-being of a particular subject, this issue should be discussed with the medical monitor for this study and the subject's participation in the study may be discontinued.

Discontinuation of treatment should be considered if:

- ALT or AST $> 8 \times$ ULN
- ALT or AST $> 5 \times$ ULN for more than 2 weeks
- ALT or AST $> 3 \times$ ULN and total bilirubin $> 2 \times$ ULN or international normalized ratio (INR) > 1.5
- ALT or AST $> 3 \times$ ULN with the appearance of fatigue, nausea, vomiting, right upper quadrant pain or tenderness, fever, rash, and/or eosinophilia (differential count $> 5\%$)

In the event that ALT or AST is $> 3 \times$ ULN, the subject will return for an unscheduled clinic visit, and blood will be drawn for a coagulation panel to determine the INR. The INR will be determined at a local laboratory.

All subjects discontinued from the study should be followed until abnormal values return to normal, and all discontinuations should be discussed with the medical monitor prior to discontinuation.

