3.1 Study Design

This is a multicenter, Phase 2, open-label extension study that will assess the long-term safety and tolerability of GTx-024.

The current study will enroll the following subjects from G201002:

- From the first 225 subjects enrolled in G201002, only subjects randomly assigned to the placebo group and who have completed the 12-week treatment period and 16-week durability period will be allowed to enroll in this study, once data from G201002 are unblinded. Placebo subjects who enrolled in the durability extension study (G201003) will be allowed to discontinue participation in G201003, once data from G201002 have been unblinded
- From Subject 226 onwards, any subject who was randomly assigned to any treatment group and who has completed the 12-week treatment period and the 4-week follow-up period in Study G201002

All subjects in this study will receive GTx-024 3 mg orally, once daily.

The study consists of the following visits:

Baseline (Day 0)

Subjects will be evaluated, and an additional written informed consent for the open-label extension study will be obtained. Procedures will be performed at baseline as specified in the schedule of events (Table 12–1) for the study.

Long-term Open-label Extension Period

Subjects who continue to meet the eligibility criteria will attend clinic visits at 4-week intervals for the first 12 weeks of the open-label extension study (i.e., Weeks, 4, 8, and 12). Following the first 12 weeks, subjects will attend clinic visits every 12 weeks (i.e., 12 weeks from Visit 3 onwards). At each clinic visit, study procedures will be performed as specified in the schedule of events (Table 12–1).

There is currently no planned end to this study; instead, subjects will be on treatment and followed until marketing approval is granted to GTx-024 or until the withdrawal of the Investigational New Drug application. If marketing approval is granted to GTx-024, a plan

for the transition of subjects from study drug to commercial drug product or other therapy will be implemented.

Data from this open-label extension study will be used to assess the long-term safety and tolerability of GTx-024.

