3.1.1.1 Risk Mitigation

This study has been designed to mitigate known risks associated with the use of GTx-024. Clinical study G200501 observed the effects of administering doses of 0.1, 0.3, 1, and 3 mg of GTx-024 (or placebo) for 86 days to healthy subjects: postmenopausal women and elderly men. Dose-dependent increases in serum alanine aminotransferase (ALT) and aspartate aminotransferase (AST) were observed. A higher incidence of transient, asymptomatic increases in ALT levels reported as AEs occurred in the group receiving GTx-024 3 mg (20.8%) compared with the placebo group (0%). One subject who received 3 mg/day of GTx-024 was discontinued due to an ALT level >3 times the upper limit of normal (ULN). The ALT levels returned to normal with continued exposure to GTx-024 in most cases and, furthermore, in instances when dosing was not continued, levels returned to normal. No significant increases in levels of total bilirubin, gamma glutamyl transferase, alkaline phosphatase, or lactate dehydrogenase have been observed in subjects with elevated ALT levels. Consistent with the effects of other orally administered anabolic agents, GTx-024 causes a dose-dependent reduction in high-density lipoprotein (HDL), the clinical significance of which is unknown at this time. The proposed mechanism for reduction in HDL is due to stimulation of reverse cholesterol transport and increased HDL catabolism by hepatic lipase. Reductions in HDL levels are temporary and typically return to baseline levels 12 months after treatment initiation.

In an ongoing, Phase 2 study of GTx-024 in estrogen receptor-positive/androgen receptor-positive breast cancer that is examining daily doses of GTx-024 at 9 and 18 mg, several cases of clinically significant hypercalcemia have been observed that were assessed by the investigators as possibly related to GTx-024. Subjects with hypercalcemia had

estrogen receptor–positive breast cancer with bone metastases. Hypercalcemia has not been observed in previous studies of healthy individuals or at doses <9 mg.

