Subjects will be monitored at each visit for health changes since the previous visit and adverse effects of treatment. Since elevations in ALT levels have been observed in prior studies, serum ALT and other liver function analytes will be monitored at each visit during treatment (Table 12–1). Stopping rules have been included for severe elevations of liver function tests or other signs of hepatotoxicity (Section 6.3.2). Subjects will also be monitored for changes in lipid profile and serum calcium.

The effect of GTx-024 on a fetus has not been evaluated; therefore, the subjects in the current investigation will be postmenopausal.

4 Subject Selection and Withdrawal Criteria

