5.4.1 Study Drug Packaging and Storage

Study drug will be packaged in high-density polyethylene bottles with induction seal and child-resistant closure. Each bottle will contain sufficient study drug for 35 days of dosing according to the study protocol. Three bottles (a total of 105 dosing days) will be packaged together in one subject kit. For the first 3 visits, sites will collect the study drug previously dispensed, perform accountability, and re-dispense the same kit.

Each subject kit, and the bottles contained in the kit, will be labeled with a unique medication identification number. A clinical label with the medication identification number will be affixed to the outside of each bottle and subject kit. The label will also specify storage and dosing information.

At the study site, study drug must be stored in a secure area (e.g., a locked cabinet), protected from moisture, and kept at a controlled room temperature of 15°C to 25°C (59°F-77°F), with excursions permitted to 30°C (86°F).

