6.6 Laboratory Analyses

Any abnormal laboratory test results or other safety assessments, including those that worsen from baseline, felt to be clinically significant in the medical and scientific judgment of the investigator are to be recorded as AEs or SAEs.

However, any clinically significant safety assessments that are associated with the underlying disease, unless judged by the investigator to be more severe than expected for the subject's condition, are **not** to be reported as AEs or SAEs.

Laboratory analyses include the following:

- Complete blood count, including red blood cells, white blood cells, mean corpuscular volume, hemoglobin, hematocrit, platelets, and differential (basophils, eosinophils, lymphocytes, monocytes, and neutrophils)

- Comprehensive metabolic panel (Chem 16), including calcium, carbon dioxide, glucose, potassium, sodium, total protein, and kidney and liver function tests (serum ALT, AST, γ -glutamyl transpeptidase, and total and direct bilirubin) will be performed (the investigator may repeat these checks if clinically indicated)
- Fasting lipid panel, including total cholesterol, low-density lipoprotein, HDL, and triglycerides
- Hormone panel, including testosterone, free testosterone, and estradiol
- SHBG

7 Statistical and Analytical Plan

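### Section 6.3.2 makes ALT or AST above 5 × ULN for more than 2 weeks a criterion for considering discontinuation but sets no timed repeat test; after Week 12 the next required test is 70–98 days away

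*Combined protocol and SAP*

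**What the plan says.** Section 6.3.2 gives four liver criteria for considering discontinuation. The second depends on duration: ALT or AST above 5 × "ULN for more than 2 weeks". Once ALT or AST exceeds 3 × ULN, "the subject will return for an unscheduled clinic visit, and blood will be drawn for a coagulation panel to determine the INR". No time limit is attached to that visit, and ALT, AST and bilirubin are not named.

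Other provisions on liver testing:

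- Section 3.1.1.1 says that "serum ALT and other liver function analytes will be monitored at each visit during treatment" and refers to Table 12-1.
- Table 12-1 has the metabolic panel, which includes ALT and AST, in all six visit columns. None of the six is for an unscheduled visit.
- Section 3.1: "Following the first 12 weeks, subjects will attend clinic visits every 12 weeks".
- Section 6.6, on the metabolic panel: "the investigator may repeat these checks if clinically indicated".
- Sections 6.3.1.3, 6.3.1.4 and 6.3.1.6 require adverse events to be followed to resolution or stability, with changes in severity documented.

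On supply, Section 5.4.1 says "Three bottles (a total of 105 dosing days) will be packaged together in one subject kit", and Section 6.1.3, for Week 24 onwards, says "Study drug will be dispensed, with administration instructions, at each clinic visit".

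**The concern.** A duration criterion works only if something makes the second measurement happen soon after the duration has elapsed. Here the triggered visit may fall on any day and supplies an INR. INR is the one laboratory input to the criteria that the routine panels lack, so naming it is sensible, but it does not show whether ALT is still above 5 × ULN.

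The stake is subject safety during open-ended dosing. Section 3.1.1.1 names ALT elevation as a known risk at 3 mg and presents the stopping rules as part of the mitigation. It also says that most rises resolved with continued exposure. Separating a transient rise from a persistent one is what the criterion is for, and a repeat at a set time is what would do it. The study has no comparator group and no formal testing, so no between-group inference is affected.

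**Working it through.** The plan states no figure for this point, so there is none to reproduce. The check has two parts.

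**1. Does any provision require a repeat ALT/AST soon after day 14?**

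- *Unscheduled visit (6.3.2).* A value above 5 × ULN is also above 3 × ULN, so the subject must return. The visit is undated and only the INR is named.
- *Monitoring at each visit (3.1.1.1).* The sentence points to Table 12-1, which has no unscheduled column. Even if it is read to cover that visit, a draw on days 1–14 cannot show more than 2 weeks.
- *Repeat panel (6.6).* Optional and undated.
- *Follow-up until values normalise (6.3.2).* Covers subjects already discontinued, not those still dosing.
- *Adverse-event follow-up (6.3.1.3, 6.3.1.4, 6.3.1.6).* No test and no date. It applies if the value is recorded as an adverse event, which 6.6 ties to the investigator judging it clinically significant.
- *Scheduled panels (Table 12-1).* These do require a later value. The question is when.

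**2. How late is the scheduled value?**

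Inputs: threshold 14 days (6.3.2); spacing 28 days to Week 12 and 84 days after it (3.1, Table 12-1); window ±7 days at each visit after baseline, none at baseline (Table 12-1); 3 bottles of 35 days per kit (5.4.1).

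Gap = nominal spacing ± the sum of the two visits' windows. Delay = gap − 14.

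| Raised value found at | Gap to next required ALT/AST (days) | Past the 14-day threshold (days) |
|---|---|---|
| Baseline | 28 ± 7 = 21–35 | 7–21 |
| Week 4 or Week 8 | 28 ± 14 = 14–42 | 0–28 |
| Week 12 or later | 84 ± 14 = 70–98 | 56–84 |

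A gap of exactly 14 days does not satisfy more than 2 weeks. If visits are instead counted from the actual previous visit, the last row becomes 84 ± 7 = 77–91 days, which is 63–77 days past the threshold.

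The last row applies when ALT is not rechecked at the unscheduled visit, or is rechecked only on days 1–14.

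*Drug on hand.* 3 × 35 = 105 dosing days; 105 − 98 = 7 days to spare over the longest gap. This assumes a full kit is dispensed at Week 12 and at each later visit.

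*Gain from a repeat on days 15–21.* The answer comes between 70 − 21 = 49 and 98 − 15 = 83 days before the next scheduled draw.

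**The case against.** The strongest reply is that the protocol is not silent. The metabolic panel is required at every scheduled visit, so a later ALT/AST always comes while the subject stays in the study, and up to Week 12 it comes within about two to six weeks. A clinically significant value is to be recorded as an adverse event and followed to resolution. Section 6.3.1.4 asks for severity changes to be documented so that the duration at each grade can be assessed, which is close to the question the criterion asks. A subject above 3 × ULN must be seen. Section 6.3.2 also lets the investigator take concerns to the medical monitor at any time, and the criteria only ask that stopping be considered.

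Much of this stands. It confines the problem mainly to values found at Week 12 or later, and it means a careful investigator would probably retest. It does not supply the missing value. The follow-up duties carry no test and no day count, depend on a judgment of clinical significance, and may end once the event is deemed chronic, stable or not clinically significant. Even a discretionary review of the 2-week criterion needs a measurement after day 14.

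The reply is also right about the risk figure. The 20.8% at 3 mg (0% on placebo) in Section 3.1.1.1 counts transient, asymptomatic ALT increases reported as adverse events. It is not a rate above 3 × or 5 × ULN. It comes from an 86-day study, about the length of the 4-weekly testing period here. The same section reports one 3 mg subject discontinued for ALT above 3 × ULN.

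**Conclusion.** The point holds as a gap in timing. From Week 12 on, the 2-week criterion cannot be judged on time from the tests the protocol requires: the next one is 70–98 days after the raised value, 56–84 days past the threshold, while the subject has drug to continue. Before Week 12 the schedule largely covers the criterion, with a delay of up to 28 days. This rests on the visit windows in Table 12-1, a full kit at each visit from Week 12, and no optional retest after day 14. The documents give no expected number of subjects above 5 × ULN, and none is assumed.

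A reader might infer more than the documents support:

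- *That no second value is ever required.* Table 12-1 requires one; after Week 12 it comes late.
- *That a site could ignore a raised ALT without any deviation.* The adverse-event duties may oblige follow-up, though not a dated liver test.
- *That a routine examination row is needed because the criteria include right upper quadrant tenderness and rash.* The synopsis and Section 6.3.3 list a physical examination that has no row in Table 12-1. That is a minor inconsistency. Examinations at fixed early visits would not find signs that appear when ALT rises later.

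**What to change.** Amend Section 6.3.2:

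1. Set a time limit for the unscheduled visit above 3 × ULN, for example within 7 days of the result; the limit is the sponsor's choice. At that visit require repeat ALT, AST and total bilirubin with the INR, a symptom check, and a targeted examination of the abdomen and skin.
2. If ALT or AST exceeds 5 × ULN and drug continues, require a repeat ALT/AST on days 15–21 after the first value. A scheduled draw that falls in that window counts.

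The cost is one or two extra liver tests per affected subject, the first on a blood draw already required, a short examination at the unscheduled visit, and possibly one extra visit for the day 15–21 repeat. Only subjects above 3 × or 5 × ULN carry it. As housekeeping, reconcile the physical examination listed in the synopsis and Section 6.3.3 with Table 12-1; this fix does not need a routine examination row.
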